6.6 Diet/Activity/Other Considerations

6.6.1 Diet

Subjects should maintain a normal diet unless modifications are required to manage an AE such as diarrhea, nausea or vomiting.

6.6.2 Contraception

Nivolumab and ipilimumab may have adverse effects on a fetus in utero. Furthermore, it is not known if nivolumab or ipilimumab have transient adverse effects on the composition of sperm. Non-pregnant, non-breast-feeding women may be enrolled if they are willing to use 2 methods of birth control or are considered highly unlikely to conceive. Highly unlikely to conceive is defined as 1) surgically sterilized, or 2) postmenopausal (a woman who is \geq 45 years of age and has not had menses for greater than 1 year will be considered postmenopausal), or 3) not heterosexually active for the duration of the study. The two birth control methods can be either two barrier methods or a barrier method plus a hormonal method to prevent pregnancy. Subjects should start using birth control from study Visit 1 throughout the study period up to 120 days after the last dose of study therapy.

The following are considered adequate barrier methods of contraception: diaphragm, condom (by the partner), copper intrauterine device, sponge, or spermicide. Appropriate hormonal contraceptives will include any registered and marketed contraceptive agent that contains an estrogen and/or a progesterone agent (including oral, subcutaneous, intrauterine, or intramuscular agents).

Subjects should be informed that taking the study medication may involve unknown risks to the fetus (unborn baby) if pregnancy were to occur during the study. In order to participate in the study, they must adhere to the contraception requirement (described above) for the duration of the study and during the follow-up period. If there is any question that a subject will not reliably comply with the requirements for contraception, that subject should not be entered into the study.

6.6.3 Use in Pregnancy

If a subject inadvertently becomes pregnant while on study, the subject will immediately be removed from the study. The treating investigator and/or their designee will contact the subject at least monthly and document the subject's status until the pregnancy has been completed or terminated. The outcome of the pregnancy will be reported to the Principal Investigator.

If a male subject impregnates his female partner the study personnel at the site must be informed immediately and the pregnancy reported to the Principal Investigator and followed as described above.

6.6.4 Use in Nursing Women

There are no data on the presence of nivolumab or ipilimumab in human milk, the effects on the breastfed child, or the effects on milk production. Because of the potential for serious adverse reactions in breastfed children and since many drugs are excreted in human milk, subjects who are breast-feeding are not eligible for enrollment.

6.7 Subject Withdrawal/Discontinuation Criteria

Subjects may withdraw consent at any time for any reason or be dropped from the trial at the discretion of the principal and/or treating investigator should any untoward effect occur. In addition, a subject may be withdrawn by the principal and/or treating investigator if enrollment into the trial is inappropriate, the trial plan is violated, or for administrative and/or other safety reasons. Further details are described in Section 4.7.

6.8 Clinical Criteria for Early Trial Termination

Early trial termination will be the result of the criteria specified below:

1. Quality or quantity of data recording is inaccurate or incomplete
2. Poor adherence to protocol and regulatory requirements
3. Incidence or severity of adverse drug reaction in this or other studies indicates a potential health hazard to subjects
4. Plans to modify or discontinue the development of the study drug
5. If 2 patient deaths attributed to the investigational drug are seen in the 30 days following surgery. The relationship of the investigational drug to the mortality will be determined by the treating medical oncologist and surgeon.
6. Assuming a major complication rate of 10% from the combination immunotherapy (Taioli, 2015), the trial will be halted if any major complication which is attributed to the investigational drug occurs in the first two patients, or in 3 cases among the first 11 patients, or in any 4 patients during the course of the trial. In order for the trial to be halted, these complications must be determined to result from the investigational drug as will be determined by the treating oncologist and surgeon. A composite adverse event of major complications defined as the occurrence of any ventricular arrhythmia requiring treatment, hemorrhage requiring re-operation, acute respiratory distress syndrome (ARDS), pneumonia, reintubation, placement of a tracheostomy, pulmonary embolus, empyema, sepsis, intra-abdominal sepsis, myocardial infarction and unexpected return to the operating room will be monitored sequentially.

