Patients undergoing CRS+HIPEC have an overall median survival of 53 months, with a more favorable prognosis for patients that undergo a complete cytoreduction (CC-0/1)(Yan TD 2009). The agent of choice for the intra-operative chemotherapy is either platinum based (cisplatin/carboplatin) or mitomycin C (Helm, 2015). Grade III-IV complication rates after this surgery can be as high as 31-40% (Kepenekian 2016). Major complications include death, anastomotic leak, deep or superficial site infection, anemia, re-operations, organ failure including renal failure, cardiac failure or respiratory failure, neutropenia, thromboembolic events, dehydration and failure to thrive.

Due to the relatively low incidence of peritoneal mesothelioma, there are no large randomized controlled trials for either surgery or chemotherapy to guide management, leaving no clear consensus on optimal treatment approach. Therefore, much of the management is extrapolated from the studies in pleural mesothelioma. Standard chemotherapy for pleural mesothelioma consists of pemetrexed plus cisplatin. This regimen was FDA-approved for MM based on a single-blind, placebo-controlled, phase III trial, which randomized 456 patients to cisplatin with or without pemetrexed. Patients who received the combination achieved a longer median overall survival (12.1 vs. 9.3 months, $p = 0.020$), a superior time to progression (5.7 vs. 3.9 months, $p = 0.001$), and a higher objective response rate (41% vs. 17%, $p < 0.001$) than patients who received cisplatin alone (Vogelzang, 2003).

However, the benefits of cytotoxic chemotherapy for peritoneal mesothelioma are less clear and alternative therapies such as immunotherapy warrant investigation. PD-1/PD-L1 and CTLA4 are immune checkpoints that mediate immune evasion in a wide spectrum of tumors. While the normal function of PD-1 and CTLA4 is to counteract excessive immune responses directed against normal tissues, various types of cancer have manipulated this function by up-regulating the natural ligands of these checkpoints to evade immune recognition. The critical role of this pathway became evident with the promising results of clinical trials of PD-1/PD-L1 and CTLA4 inhibitors, such as pembrolizumab (Hamid, 2013), nivolumab (Wolchok, 2013), and MPDL3280A (Powderly, 2013). While immune checkpoint blockers have not been evaluated in mesothelioma in the neoadjuvant setting, they are being used safely in the preoperative setting in a variety of tumor types.

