10.5 Quality Management System

The Principal Investigator will ensure that trial is conducted and data are generated, documented, and reported in compliance with the protocol, accepted standards of Good Clinical Practice, and all applicable federal, state, and local laws, rules and regulations relating to the conduct of the clinical trial.

A quality assurance audit/inspection of this study may be conducted by regulatory authorities. The quality assurance auditor will have access to all medical records, the investigator's study-related files and correspondence, and the informed consent documentation of this clinical study.

The trial will be monitored in the weekly mesothelioma multidisciplinary conference.

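### Section 6.8 has no numeric trigger for the total operative complication rate: both numeric safety rules count only events the treating team attributes to the drug

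*Combined protocol and SAP*

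**What the plan says.** All references are to the combined protocol and SAP.

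- **Section 6.8, item 6.** The rule starts from an assumed drug-related rate: "Assuming a major complication rate of 10% from the combination immunotherapy". One boundary is met when "any major complication which is attributed to the investigational drug occurs in the first two patients". Two later boundaries are 3 attributed cases by the eleventh patient and 4 at any point. The composite includes bleeding that needs re-operation, reintubation, pneumonia, pulmonary embolus, sepsis and an unplanned return to theatre. On attribution, a judgement left to the patient's own oncologist and surgeon: "In order for the trial to be halted, these complications must be determined to result from the investigational drug".
- **Section 6.8, item 5**, repeated in section 8.2, has the same condition: "If 2 patient deaths attributed to the investigational drug are seen in the 30 days following surgery".
- **Section 6.8, item 3** allows termination when the incidence or severity of adverse drug reactions points to a hazard. It gives no number. Section 7.17.2.3 defines an adverse reaction by evidence of causality, and accepts as evidence a pooled finding that particular events occur more often than expected.
- **Section 3.2.1** gives the surgical background: "Grade III-IV complication rates after this surgery can be as high as 31-40" percent. Sections 3.2.1 and 5.3 list re-operation, infection, respiratory failure and thromboembolism among the complications of the operation itself.
- **Section 2.2, objective 1** measures grade III/IV events up to 30 days after surgery with no attribution condition. Section 8.2 makes the secondary analyses mainly descriptive and sets no boundary on that rate.
- **Section 10.5** on oversight: "The trial will be monitored in the weekly mesothelioma multidisciplinary conference".

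**The concern.** Whether two doses of nivolumab and one of ipilimumab before surgery make the operation more dangerous is a central safety question for this design. Such an effect could well appear as more of the events the operation already produces. In a single-arm trial the most direct evidence for it is the total rate set against the expected background. The two rules with numbers do not look at the total rate. An event enters the count only after the treating oncologist and surgeon have assigned it to the drug, and an event assigned to surgery leaves the count.

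Section 7.17.1 has a five-level attribution scale that includes a possible category, but section 6.8 does not say which level counts as attributed. The documents describe no independent adjudication. The behaviour of the rule therefore rests on an attribution share that is neither specified nor observable. Two teams seeing the same events could reach different outcomes under item 6.

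**Working it through.** **The plan's own figure.** The documents give no operating characteristics for item 6, so there is nothing to reproduce.

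**Inputs.** From section 6.8: halt at 1 attributed event in the first 2 patients, 3 in the first 11, or 4 at any time. From section 8.1: N = 37. From section 3.2.1: surgical background 31-40%, grade III-IV. Assumed: one yes/no composite event per patient, independent patients, and each event attributed with the same probability f.

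**Method.** Counted rate = true rate × f. P(halt) comes from an exact patient-by-patient recursion. It carries forward the probability of each running count and removes any path that meets a boundary. The first-two clause can be read as either patient or as both, so both readings are shown.

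**Step 1: a true 20% drug-caused rate.**

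| Share attributed f | Counted rate | P(halt), either of first 2 | P(halt), both of first 2 |
|---|---|---|---|
| 1.00 | 0.20 × 1.00 = 0.20 | 0.962 | 0.956 |
| 0.50 | 0.20 × 0.50 = 0.10 | 0.572 | 0.519 |
| 0.25 | 0.20 × 0.25 = 0.05 | 0.186 | 0.116 |

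**Step 2: total complications rise from 40% to 60%** (assumed rates; 37 × 0.40 = 14.8 and 37 × 0.60 = 22.2 patients). The share f now applies to all events at the 60% rate.

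| f | Counted rate | P(halt), either of first 2 | P(halt), both of first 2 |
|---|---|---|---|
| 0 | 0 | 0 | 0 |
| 0.05 | 0.03 | 0.08 | 0.03 |
| 0.10 | 0.06 | 0.26 | 0.19 |
| 0.25 | 0.15 | 0.85 | 0.83 |
| 0.50 | 0.30 | 0.999 | 0.999 |

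With no rise at all (40%) and a quarter attributed, the counted rate is 0.40 × 0.25 = 0.10 and P(halt) is already 0.57 (0.52 if both of the first two are needed). The rule follows attribution practice more than total morbidity, in both directions.

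**Step 3: could the attribution condition simply be deleted?** No. Applying the item 6 boundary to all events gives P(halt) = 0.999 at 31% and above 0.999 at 40%. An all-cause check needs its own boundary, set against the surgical background.

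**Step 4: is a workable boundary possible at this size?** As an illustration only, suppose review follows 8 complications in the first 12 operated patients, 14 in the first 24 or 20 in the first 36. This is an exact sequential binomial calculation.

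| True rate | P(review), at least 36 operated | P(review), 30 operated (third look not reached) |
|---|---|---|
| 31% | 0.016 | 0.015 |
| 40% | 0.103 | 0.088 |
| 45% | 0.23 | 0.18 |
| 50% | 0.42 | 0.33 |
| 55% | 0.63 | 0.51 |
| 60% | 0.82 | 0.69 |

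The figure of 30 operated patients is an assumption. Section 2.2, objective 2 itself anticipates that some patients will not proceed to surgery.

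**The case against.** The best defence is that the plan is not blind to an excess. Item 3, read with section 7.17.2.3, lets an aggregate excess over expectation count as an adverse reaction without labelling individual cases. Section 6.8 says the composite is followed sequentially, section 8.2 says safety is assessed throughout with the surgeon, and the conference meets weekly. This stands. A reader might infer that the plan has no route at all from a rise in morbidity to a review, and the documents do not support that. What they lack is a number on that route and anything that obliges a review.

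A reader might also infer that drug causation cannot be judged case by case. That is an inference from overlapping event types and a single arm, not something the documents establish. If the possible category counts as attributed, the condition could be quite wide. What the text shows is that the qualifying level is undefined.

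The zero halt probability is likewise only the extreme in which every event is called surgical. If a quarter of events at a 60% rate are attributed, the rule halts with probability 0.85, and nothing in the documents suggests attribution would be near zero.

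Finally, the 31-40% is an upper description of grade III-IV surgical complications. It is not the background rate of the item 6 composite, which the documents do not give. A check that counted any grade III or higher adverse event would be wider than the benchmark. If that wider background were 45% or 50% (assumed), the illustrative boundary would call an unnecessary review 23% or 42% of the time. This limits how a check should be defined, but it does not supply the missing threshold.

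**Conclusion.** The point holds as a gap in section 6.8. Neither numeric trigger responds to the total operative complication rate, and the one attribution-free route has no threshold and compels no review. The size depends on the share attributed: for a true 20% drug-caused rate, P(halt) runs from 0.96 (all attributed) through 0.57 (half) to 0.19 (a quarter). The alternative reading of the first-two clause gives 0.96, 0.52 and 0.12, so the conclusion does not turn on it.

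These figures assume independent patients, one event per patient and a constant attribution share. The share itself is unknown, which is why a range is shown. An attribution condition of some kind is needed with the current item 6 boundary, so the remedy is an addition and not a deletion. This is a change that should be made. It does not invalidate the design.

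**What to change.** Keep item 6. Reconcile section 6.8 with section 7.17.2.3 and with section 2.2, objective 1 by adding one trial-level, attribution-free check:

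- **Count** operated patients with a grade III or higher post-operative complication within 30 days. Use the same event definition as the source of the 31-40% benchmark, and say whether deaths are included in that benchmark.
- **Consequence:** a documented review at the existing weekly conference, not an automatic halt.
- **Boundary:** chosen by the sponsor, with the probabilities of a false review and of detection stated for the number of patients expected to reach surgery. The 8/12, 14/24, 20/36 scheme above only shows that useful properties are attainable.
- **Clarify** which levels of the section 7.17.1 scale count as attributed in items 5 and 6, and whether the first-two clause means either patient or both.

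The cost is about one paragraph in sections 6.8 and 8.2. It uses 30-day events that objective 1 already needs and a conference that already meets. The downside is an occasional unnecessary review. Under the illustration this is about 10% at a true 40% rate and 2% at 31%, and more if the counted events are wider than the benchmark's. Detection falls if fewer patients are operated on: 0.69 instead of 0.82 at a 60% rate with 30 operated.

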7.0 TRIAL PROCEDURES

7.1 Flow Chart – Schedule of Events

7.1.1 Flow Chart for Screening, Neoadjuvant, and Surgery Phases

Table 2. Trial Flow Chart of Screening, Neoadjuvant, and Surgery Phases

Trial Phase:	Screening Phase	Neoadjuvant Treatment Phase		Pre-Surgery Phase	Surgery Phase	Post-Surgery Recovery Phase
	Screening (Visit 1)	C1 D1	C1 D22C	4 Weeks	3 Weeks	3-4 Weeks
Scheduling Window (Days):	-28 to -1		± 3			
Administrative Procedures						
Informed Consent	X					
Inclusion/Exclusion Criteria	X			X	X	
Demographics and Medical History	X			X	X	
Prior and Concomitant Medication Review	X	X	X	X	X	
Interventions						
Nivolumab Administration		X	X			
Ipilimumab Administration		X				
Surgery					X	
Clinical Procedures/Assessments						
Review Adverse Events	X	X	X	X		
Full Physical Examination	X	X	X	X	X	
Height	X					
Vital Signs and Weight	X	X	X	X	X	
ECOG Performance Status	X	X	X	X	X	
EORTC QOL C30	X			X		X
Surgeon Assessment	X			X		
Medical Oncology Assessment	X	X	X	X		
Laboratory Procedures/Assessments: analysis performed by LOCAL laboratory ^a						
Pregnancy Test – Urine or Serum β-HCG	X					
CBC with Differential	X	X	X	X		
Comprehensive Serum Chemistry Panel	X	X	X	X		
INR, PTT	X			X		
Urinalysis	X					
TSH (reflex T3, T4 if abnormal)	X	X		X		
Efficacy Measurements ^b						
Tumor Imaging with CT/MRI	X			X		
CA-125	X			X		
Circulating tumor cells	X			X		
Tumor Biopsies/Archival Tissue Collection/Correlative Studies Blood						
Laparoscopy for tissue and PCI score assessment	X					
Correlative Studies Blood Collection ^c	X	X		X	X	

a. Screening lab tests to be performed within 14 days before first dose. After Cycle 1, pre-dose lab procedures can be conducted <72 hours before dosing.
 b. For CT scans, scheduling window is +/- 7 days.
 c. Serum mesothelin and osteopontin will be obtained at the times of tumor imaging and upon tumor progression.

7.1.2 Flow Chart for Adjuvant and Post-Treatment Phases

Table 3. Trial Flow Chart of Adjuvant and Post-Treatment Phases

Trial Period:	Adjuvant Therapy Phase								End of Treatment	Post-Treatment Phase			
	Treatment Week/Title:		C1 D1	C1 D22	C2 D1	C2 D22	C1 D1	C1 D22	C2 D1	C2 D22	Safety Follow-up	Follow Up Visits	Survival Follow-Up
Scheduling Window (Days) ^c :		± 3	± 3	± 3	± 3	± 3	± 3	± 3	± 3	At time of Discon	30 days post discon	Every 12 wks post discon	Every 12 weeks
Nivolumab Administration	X	X	X	X	X	X	X	X	X				
Ipilimumab Administration		X		X									
Prior and Concomitant Medication Review	X	X	X	X	X	X	X	X	X	X			
Post-study anticancer therapy status									X				
Survival Status									X	X	X	X	
Review Adverse Events	X	X	X	X	X	X	X	X	X	X	X	X	X
Full Physical Examination	X	X	X	X	X	X	X	X	X				
Vital Signs and Weight	X	X	X	X	X	X	X	X	X				
ECOG Performance Status	X	X	X	X	X	X	X	X	X				
EORTC QOL C30	X		X		X		X		X	X			
Laboratory Parameters													
CBC with Differential	X	X	X	X	X	X	X	X					
Comprehensive Serum Chemistry Panel	X	X	X	X	X	X	X	X					
TSH (reflex T3, T4 if abnormal)	X		X		X		X						
Efficacy Measurement													
Tumor Imaging with CT scan every 12 weeks ^c	X		X		X		X						
CA-125	X		X		X		X						
Circulating tumor cells	X		X		X		X						
Correlative Lab													
Correlative Studies Blood Collection ^{a,b}	X				X				X				
a. Both tumor imaging and correlative studies to be repeated after every 6 weeks. b. Serum mesothelin and osteopontin will be obtained at the times of tumor imaging and upon tumor progression. c. For CT scans, the scheduling window is +/- 7 days													

The Trial Flow Chart summarizes the trial procedures to be performed at each visit. Individual trial procedures are described in detail below. It may be necessary to perform these procedures at unscheduled time points if deemed clinically necessary by the investigator.

7.2 Informed Consent

The Investigator must obtain documented consent from each potential subject prior to participating in a clinical trial.

Consent must be documented by the subject's dated signature or by the subject's legally acceptable representative's dated signature on a consent form along with the dated signature of the person conducting the consent discussion.

A copy of the signed and dated consent form should be given to the subject before participation in the trial.

The initial informed consent form, any subsequent revised written informed consent form and any written information provided to the subject must receive the IRB/ERC's approval/favorable opinion in advance of use. The subject or his/her legally acceptable representative should be informed in a timely manner if new information becomes available that may be relevant to the subject's willingness to continue participation in the trial. The communication of this information will be provided and documented via a revised consent form or addendum to the original consent form that captures the subject's dated signature or by the subject's legally acceptable representative's dated signature.

The informed consent will adhere to IRB/ERC requirements and applicable laws and regulations.

7.3 Inclusion/Exclusion Criteria Review

All inclusion and exclusion criteria will be reviewed by the treating investigator or qualified designee to ensure that the subject qualifies for the trial.

7.4 Medical History

A medical history will be obtained by the treating investigator or qualified designee. Medical history will include all active conditions, and any condition diagnosed within the prior 10 years that are considered to be clinically significant by the Investigator. Details regarding the disease for which the subject has enrolled in this study will be recorded separately and not listed as medical history.

7.5 Prior and Concomitant Medications Review

7.5.1 Prior Medications

The treating investigator or qualified designee will review prior medication use, including any protocol-specified washout requirement, and record prior medication taken by the subject within 28 days before starting the trial. Treatment for the disease for which the subject has enrolled in this study will be recorded separately and not listed as a prior medication.

